A prospective randomized trial comparing restorelle Y mesh vs. restorelle dual flat mesh for laparoscopic and robotic-assisted laparoscopic sacrocolpopexy

[name] MPH; Fellow in Female Pelvic Medicine and Reconstructive Surgery. Center of Urogynecology and Pelvic Floor Disorders; Obstetrics/Gynecology and Women's Health Institute at the Cleveland Clinic

[name]; Assistant Professor, Center of Urogynecology and Pelvic Floor Disorders; Obstetrics/Gynecology and Women's Health Institute at the Cleveland Clinic

[name]; Assistant Professor, Center of Urogynecology and Pelvic Floor Disorders; Obstetrics/Gynecology and Women's Health Institute at the Cleveland Clinic

[name] [name]; Professor, Section Head of the Center of Urogynecology and Pelvic Floor Disorders; Obstetrics/Gynecology and Women's Health Institute at the Cleveland Clinic

Background and Significance:

Abdominal sacrocolpopexy is considered the gold standard for vault prolapse, and has demonstrated superior anatomic outcomes compared to transvaginal suspension procedures. Laparoscopic sacrocolpopexy has become an alternative to open abdominal sacrocolpopexy as this mode of surgery bridges the gap between the advantages of vaginal surgery, namely decreased morbidity and faster patient recovery, with the surgical success rates of abdominal sacrocolpopexy (1). For young women who are sexually active with symptomatic pelvic organ prolapse, reconstruction with a sacrocolpopexy procedure is beneficial because the success rates are high as the procedure adequately restores support of the vaginal apex and maintains vaginal length (2). Robotic-assisted laparoscopic sacrocolpopexy has also emerged as a mode of vaginal vault prolapse surgery, and is a good option for patients with significant body mass index, or known pelvic adhesive disease that may make a conventional laparoscopic approach more challenging.

Sacrocolpopexy involves suspension of the vagina to the anterior longitudinal ligament of the sacrum at the level of S1 using a bridging graft which can be made of biologic or synthetic materials. The graft is sutured to the anterior as well as the posterior vagina and then attached to the anterior longitudinal ligament of the sacrum. There are a number of prosthetic materials available for use in pelvic reconstructive surgery, including sacrocolpopexy. Mersilene was a popular prosthetic for many decades, but its use rapidly declined in favor of polypropylene which is now the most commonly used synthetic product (3). The ideal prosthetic material is biocompatible, inert, has minimal allergic or inflammatory reaction, is sterile, non-carcinogenic, resistant to infection, and avoids shrinkage and mechanical stress and is easy to handle and readily available at a reasonable cost (4). Additionally, pore size of the graft material affects resistance to infection and cellular infiltration and also the flexibility of the mesh (5). Lastly, the interaction at the tissue interface of the graft material is also very important, with the

ideal prosthesis causing minimal initial inflammatory and cellular response followed by adequate vascular and fibroblastic infiltration (6). Many different materials have been used as a graft in sacrocolpopexy including biologic materials (fascia lata, rectus fascia, dura mater) and synthetic materials (polypropylene mesh, polyester fiber mesh, polytetrafluorethylene mesh, Dacron mesh, and Silastic silicone rubber). Large pore light-weight polypropylene mesh is a monofilament graft and is most commonly used today as it meets the above-mentioned requirements, and likely has fewer complications compared to other synthetics because of these characteristics (2).

Restorelle Smartmesh (Coloplast®, Minneapolis, MN, USA) is an ultra-light macroporous polypropylene mesh graft intended for pelvic floor reconstruction. Two grafts are currently made for sacrocolposuspension: the restorelle Y mesh and the restorelle flat mesh (L mesh). The Y mesh has two arms which attach to the anterior and posterior vagina and a stem which attaches to the sacral promontory. The flat mesh is a sheet of polypropylene that comes in three sizes (Restorelle M Flat Mesh - 15cm x 10cm, Restorelle L Rectangle Flat Mesh - 24cm x 8cm, Restorelle XL Flat Mesh - 30cm x 30cm) and can be trimmed into two strips that are attached to the anterior and posterior vagina, respectively, and then sutured together to the sacral promontory. Currently, both types of grafts are used to perform sacrocolpopexy.

Cost of health care has become a hot topic in the medical community. One of the focuses of cost containment in medicine has centered around operating room efficiency. Several studies have looked at OR time nonutilization (7) in order to determine the economic value of saving OR time. Surgeons can make significant contributions to these types of savings by reducing equipment needs, facilitating case set-up times, and focusing on intraoperative efficiency. This includes choosing materials that may make certain procedures faster and more efficient. When performing a sacrocolpopexy, surgeons have the option of choosing a mesh graft configured in a Y shape, which requires introduction into the pelvis only once, and suturing of one arm to the sacral promontory; versus a dual flat mesh, which requires introduction into the pelvis twice, as there are two separate pieces to suture to the vagina, and suturing of both pieces of mesh together to the promontory. It is unclear if one version of the restorelle mesh is faster to use than the other, and if this savings in time, translates to cost savings in the operating room. The primary objective of the proposed study is to determine the difference in suturing time when using the restorelle Y mesh versus the restorelle dual flat mesh at the time of laparoscopic and robotic-assisted laparoscopic sacrocolpopexy.

Hypothesis: Suturing time when using the restorelle Y mesh will be faster than when using the restorelle dual flat mesh at the time of laparoscopic and robotic-assisted laparoscopic sacrocolpopexy.

Study Design: Randomized single-blind prospective clinical trial

Primary Outcomes:

1. Total Suturing time for mesh placement = time from insertion of Y mesh or first flat mesh arm into pelvis to last sacral suture placed
2. Total OR time = operating room time of entry and exit
3. Total Case time = Incision to end of closure

Secondary Outcomes:

1. Intraoperative, peri-operative and post-operative complications
2. Hospital costs (Y mesh v. dual mesh and stratified by RA LSC v. LSC)
3. Post-operative patient outcomes at 6 weeks, 6 months, 12 months and 24 months
 - Pelvic Organ Prolapse Quantification (POPQ) system (standardized quantification of prolapse established by the International Continence Society) – Required at 6 months; Optional but encouraged at 12 and 24 months.
 - Pelvic Floor Dysfunction Inventory (PFDI-20) – Required pre-operatively and at 6 weeks, 6, 12 and 24 months.

Study Population: Study subjects will be recruited from patients that present to the Center of Urogynecology and Pelvic Floor Disorders in the Department of Obstetrics and Gynecology at the Cleveland Clinic main campus, Hillcrest Hospital and Fairview Hospital, and their surgeries will be performed at either one of these sites.

Inclusion Criteria:

- Age \geq 18, who are to undergo laparoscopic or robotic laparoscopic sacrocolpopexy for pelvic organ prolapse
- Other concomitant laparoscopic or prolapse and anti-incontinence procedures (e.g., laparoscopic supracervical hysterectomy, cystocele repair, rectocele repair or mid-urethral sling procedures) will be performed at the primary surgeon's discretion.

Exclusion Criteria:

- Inability to comprehend written and/or spoken English
- Inability to provide informed consent
- Medical illness precluding laparoscopy
- Need for concomitant surgeries not related to pelvic organ prolapse or incontinence
- Sacrocolpoperineopexy

Study Procedures:

Study Identification and Recruitment

Potential subjects will be identified by members of the Center for Urogynecology and Pelvic Reconstructive Surgery at the Cleveland Clinic main campus and Fairview Hospital. Eligible patients that agree to participate will be provided written informed consent administered by the collaborators listed on this IRB at the Cleveland Clinic main campus and Fairview Hospital.

Randomization

All subjects will be predetermined by their surgeon to undergo either a laparoscopic or robotic assisted laparoscopic sacrocolpopexy depending upon their clinical evaluation. The participants will then be randomized to either Y mesh or dual flat mesh sacrocolpopexy according to a computer-generated randomization schedule with random block sizes with the use of the SAS statistical software package (SAS Institute, Cary, NC). Randomization will be carried out by provider. All patients will be blinded to their assignment.

Office Interventions

In addition to a standardized evaluation including the history and physical examination, patients will be asked to complete the Pelvic Floor Distress Inventory (PFDI-20) questionnaire at the pre-operative visit as well as the 6 week, 6, 12 and 24 month postoperative visit. Completion of these questionnaire is the only additional assessment that is specific to participation in this study and is not usually included as part of the standard care of sacrocolpopexy. It should take no more than 10-15 minutes to complete the questionnaire. The study subjects will not be exposed to any additional risk by participating in this study except for the inconvenience of completing the questionnaire.

Surgical Interventions

Laparoscopic sacrocolpopexy will be performed using four ports: an umbilical port for the laparoscope, two ports (either 5 or 10/12 mm) in the bilateral lower quadrants, and one 5-mm port placed at the level of the umbilicus, lateral to the rectus muscle on either side for retraction. The robotic-assisted hysterectomy will be performed using the da Vinci Surgical System (Intuitive Surgical Inc., Sunnyvale, CA, USA) using five ports: a 12mm umbilical port for the laparoscopic, two 8 mm robotic ports placed 2cm inferior and 9-10cm lateral to the umbilicus bilaterally, an 8mm robotic port placed in the left axillary line at the level of the umbilicus, and a 8mm or 10/12mm accessory port either in the right upper quadrant approximately 3cm distal from the costal margin, or in the right lower quadrant, 2cm above and medial to the anterior superior iliac spine.

If a supracervical hysterectomy is to be performed, it will be done in a standard fashion. A uterine manipulator will be placed inside of the uterus. The round ligaments will be transected using cautery. The fallopian tubes and ovaries will be left in situ or removed at the time of hysterectomy depending upon the preoperative decision made between the surgeon and patient. The uterine arteries and cardinal ligaments will be cauterized

laparoscopically. The uterus will be amputated at the level of the internal cervical os and the endocervical canal will be cauterized.

The sacrocolpopexy will also be performed and in a standard fashion. An end-to-end anastomosis (EEA) sizer will be placed in the vagina for manipulation of the apex as well as in the rectum for delineation of the rectovaginal septum. First, the presacral dissection will be performed with a longitudinal peritoneal incision over the sacral promontory and there is identification of the anterior longitudinal ligament. Dissection is then done caudally through the peritoneum and subperitoneal fat down to the level of the posterior cul-de-sac. The vagina is elevated cephalad using the EEA sizer and the peritoneum overlying the anterior vaginal apex is incised transversely, and the bladder is dissected off the anterior vagina using sharp dissection, creating a 4 to 5 cm pocket. If this plane is difficult to establish, the bladder will be filled in a retrograde fashion to find the correct dissection plane. Similarly, the peritoneum overlying the posterior vagina is incised, and dissection is then done overlying the vagina and extending into the posterior cul-de-sac, creating a 4 to 5 cm pocket. Once dissection is complete, the mesh graft is prepared. Subjects will have been randomized to either one of two mesh grafts:

1. Restorelle Y mesh

- The mesh is introduced into the pelvis through one of the ports.
- First, either then anterior or the posterior arm is fixed to the anterior or posterior vaginal wall using 5 delayed- absorbable (PDS) No. 2-0 sutures in an interrupted fashion, 1 to 2 cm apart from each other.
- The opposing arm of the graft is then attached to either the anterior or posterior vaginal wall, depending on which arm was placed first, in a similar fashion using 5 delayed- absorbable (PDS) No. 2-0 sutures in an interrupted fashion, 1 to 2 cm apart from each other.
- The stem portion of the graft is then brought to the sacral promontory and sutured to the anterior longitudinal ligament using 2 permanent (prolene) No. 0 sutures. The excess mesh is then trimmed.

2. Restorelle dual flat mesh: 2 pieces of 15 x 4 cm mesh

- One mesh arm is introduced into the pelvis through one of the ports.
- The arm is fixed to the anterior or posterior vaginal wall using 5 delayed- absorbable (PDS) No. 2-0 sutures in an interrupted fashion, 1 to 2 cm apart from each other.
- The second mesh arm is then introduced into the pelvis through one of the ports.
- The arm is fixed to either the anterior or posterior vaginal wall, depending on where the first arm was placed, using 5 delayed- absorbable (PDS) No. 2-0 sutures in an interrupted fashion, 1 to 2 cm apart from each other.
- The two arms are then brought to the sacral promontory and sutured together to the anterior longitudinal ligament using 2 permanent (prolene) No. 0 sutures. The excess mesh is then trimmed.

The peritoneum is then closed over the exposed graft with absorbable suture.

Routine cystoscopy will also be performed in order to assess for lower urinary tract injury. A vaginal exam is performed, and an anterior and/or posterior colporrhaphy and perineorrhaphy are performed if needed. Anti-incontinence procedures may also be performed if needed.

**In laparoscopic cases, all suturing will be done extracorporeally while intracorporeal knot-tying technique will be performed in robot assisted laparoscopic cases.

Data Collection & Management:

Preoperative data will include the following:

- Patient age, race, vaginal parity, menopausal state, BMI, prior prolapse surgery, preoperative prolapse stage
- PFDI-20
- Labs (Hb/Hct)

Data points recorded during the procedure will include:

- Total OR time = operating room time of entry and exit
- Total Case time = time from incision to closure
- Total Suturing time = time from insertion of Y mesh or first flat mesh arm into pelvis to last sacral suture placed
- Level of surgeon performing suturing: Attending v. Fellow v. Both
- Concomitant procedures
 - Hysterectomy – Supracervical or Total
 - Anterior Colporrhaphy
 - Posterior Colporrhaphy
 - Perineorrhaphy
 - Midurethral Sling
- Estimated blood loss
- Intraoperative complications
 - EBL > 500cc
 - Vascular Injury
 - Cystotomy
 - Ureteral Injury
 - Bowel Injury - small bowel, large bowel, rectal

Postoperative data will include the following:

- Days in the hospital
- 6-week postoperative visit: PFDI-20
- 6-month postoperative visit (Required): POP-Q exam (performed by a provider blinded to the mesh used at the time of the procedure)
- 12 month, 24 month postoperative visit (Optional): POP-Q exam (performed by a provider blinded to the mesh used at the time of the procedure)
- 6-month, 12-month, 24-month postoperative visit: PFDI-20

- At 6, 12 and 24-months: Review of electronic medical record (inpatient notes, d/c summary, ER visits), assessing for postoperative complications
 - Reoperation for immediate complications = reoperation within 30 days of surgery
 - Abdominal Wound infection = fascial, subcutaneous, cutaneous infection requiring antibiotic treatment
 - Hematoma = intrapelvic/abdominal
 - Vaginal cuff cellulitis/Pelvic Abscess = requiring IV/PO antibiotic therapy and/or transvaginal, transgluteal or percutaneous drainage
 - DVT/PE = diagnosed with Doppler US or CT scan
 - Reoperation for SUI with pubovaginal sling (synthetic or fascial), colposuspension, injection with periurethral bulking agents
 - Reoperation for mesh exposure
 - Reoperation for recurrent POP
 - Bowel Injury/Bowel Obstruction = enterotomy, perforation, ileus, partial/complete obstruction
 - Port site or incisional hernia
 - Need for any radiologic imaging
 - Lower urinary tract injury = bladder, ureteral
 - Neurologic Injury = brachial plexus, abdominal wall (ilioinguinal, iliohypogastric), lower extremity (femoral, sciatic, common peroneal)
 - Pulmonary complications = pneumonia, pulmonary hypertension, pulmonary edema within 14 days of surgery
 - Cardiac = ACS, MI, HF within 14 days of surgery
 - Postoperative ICU admission

[figure not shown]
Protection of each subject's personal health information will be a priority in this study. One master excel file containing subject personal information including name and medical record number will be kept in a password-protected file, on a designated protected research drive on a password-protected computer in a locked office at the Cleveland Clinic. In that file, each subject will be assigned a subject identification number that will be used for the purposes of data collection in order to de-identify subjects.

All paper forms used for data collection will be kept in a research cabinet dedicated to this project which will be locked at all times, in a locked office at the Cleveland Clinic. All forms will contain de-identified information – identification numbers will correspond to the subjects listed in the master excel file.

All study data will be transferred and managed electronically using REDCap (Research Electronic Data Capture). Each subject will be entered into REDCap using the assigned identification number from the master excel file. REDCap is a secure, web-based application designed to support data capture for research studies, providing user-friendly web-based case report forms, real-time data entry validation, audit trails, and a de-identified data export mechanism to common statistical packages. The system was developed by a multi-institutional consortium which was initiated at Vanderbilt University and includes the Cleveland Clinic. The database is hosted at the Cleveland Clinic Research Datacenter in the JJN basement and is managed by the Quantitative Health Sciences Department. The system is protected by a login and Secure Sockets Layers (SSL) encryption. Data collection is customized for each study as based on a study-specific data dictionary defined by the research team with guidance from the REDCap administrator in Quantitative Health Sciences at the Cleveland Clinic.

Analysis Plan:

There will be 4 arms to this study: laparoscopic (robotic-assisted and conventional) sacrocolpopexy with Y mesh and laparoscopic (robotic-assisted and conventional) sacrocolpopexy with dual flat mesh. Subjects will be chosen based on surgeon preference to either undergo RA LSC ASC or conventional LSC ASC. They will then be randomized to either a Y mesh arm or a Dual Mesh arm. We determined that 9 subjects in each arm were needed to detect a difference of 30 minutes or more in suturing time between the two groups with 80% power and a significance level of .05. We will account for potential subject drop out and loss to follow-up as well as unforeseen factors in recruiting and will plan to recruit 15 subjects to each arm, for a total of 60 subjects.

We will use descriptive statistics to show our demographic and baseline data: categorical variables will be presented as n/N (%) with 95% confidence intervals and continuous variables will be presented as mean+/-SD [range]. Y mesh and dual mesh will be compared between the two groups (Y mesh LSC + RA LSC v. Dual mesh LSC + RA LSC). With a continuous outcome and two categorical independent factors, a two-way

analysis of variance will be used to evaluate differences between the groups. The results will be presented in a standard ANOVA table, which should be sufficient to determine if differences exist. A linear regression will be done to demonstrate actual changes in surgical time attributed to each variable. We will control for LSC ASC and RA LSC ASC by performing a logistic regression. Cost utility analysis will be used to compare the differential mean operating room costs with incremental cost effectiveness ratios (ICERs) calculated as appropriate.

Summary of tasks for study:

	Preop	O R	6 wk postop	6 mo f/u	12 mo f/u	24 mo f/u
Informed consent	X					
Demographic data	X					
Randomization	X					
PFDI-20	X		X	X	X	X
POP-Q	X			X	X ¹	X ¹
OR data collection sheet		X				
Review of d/c summary, chart, postop Hct, complications (ER visits, etc)			X	X	X	X

1. **POP-Q – Optional but encouraged at 12 and 24 months.**

References:

3. Porges RF & Smilen SW. Long term analysis of the surgical management of pelvic floor support defect. *Am J Obstet Gynecol* 1994;171:1518–1528.
4. Birch C. The use of prosthetics in pelvic reconstructive surgery. *Best Pract Res Clin Obstet Gyn* 2005;19(6):979-991.
5. Chu CC & Welch L. Characterisation of morphological and mechanical properties of surgical mesh fabrics. *J Biomed Res* 1985;19:903–916.
6. Kaupp HA, Matulewicz TJ & Lattimer GL. Graft infection or graft reaction? *Arch Surg* 1979;114:1419-1423.

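### Three operative times are listed as primary, but the objective, hypothesis and sample size cover suturing time only, and the plan never ranks the three

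*Combined protocol and SAP*

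**What the plan says.** The Primary Outcomes section numbers three items:

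- Suturing time is listed first and defined as "Total Suturing time for mesh placement = time from insertion of Y mesh or first flat mesh arm into pelvis to last sacral suture placed".
- Time in the operating room comes second, with the definition "Total OR time = operating room time of entry and exit".
- Case time comes third, with the definition "Total Case time = Incision to end of closure".

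A separate Secondary Outcomes list follows (complications, hospital costs, POP-Q and PFDI-20). Neither OR time nor case time is on it.

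Three other places name suturing time alone:

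- **Background and Significance, last paragraph:** "The primary objective of the proposed study is to determine the difference in suturing time".
- **Hypothesis:** "Suturing time when using the restorelle Y mesh will be faster than when using the restorelle dual flat mesh".
- **Analysis Plan, sample size:** "9 subjects in each arm were needed to detect a difference of 30 minutes or more in suturing time between the two groups", at 80% power and a significance level of .05.

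The Analysis Plan introduces the two-way ANOVA with the words "With a continuous outcome and two categorical independent factors" and does not identify that outcome. It adds: "The results will be presented in a standard ANOVA table, which should be sufficient to determine if differences exist". The linear regression that follows refers to surgical time without saying which of the three is meant. Data Collection & Management lists all three times as items to record and ranks none of them.

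**The concern.** The outcome list and the rest of the protocol disagree about how many primary outcomes there are. The objective, hypothesis and sample size point to one and the list gives three. Numbering items 1 to 3 does not set a hierarchy, and no text makes items 2 and 3 subordinate.

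Two misreadings of the results are left open:

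- **Too easy a success.** A significant result on OR or case time could be presented as a met primary outcome even if suturing time shows nothing. The temptation is real, because the Background motivates the trial by operating-room efficiency and cost.
- **Too easy a failure.** A null result on OR or case time could be read as a failed primary outcome. Both times include work unrelated to mesh suturing, and concomitant hysterectomy, repairs and slings are left to the surgeon's discretion. The power stated for suturing time cannot be carried over to them.

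**Working it through.** **1. The plan's own figure.** The sample size gives 9 per arm for 30 minutes, 80% power and .05, but no SD, so it can only be solved backwards. With the two-sided normal approximation, n = 2(1.960 + 0.842)² SD² / 30². Setting n = 9 gives SD = 30 × √(9 / (2 × 7.849)) = 22.7 minutes as the largest SD. The SD ranges that round up to 9 per arm are:

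| Method | SD (minutes) |
|---|---|
| Two-sided normal | 21.5 to 22.7 |
| Two-sided t | 20.0 to 21.3 |
| One-sided normal | 24.2 to 25.5 |
| One-sided t | 23.0 to 24.4 |

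The figure of 9 can be neither confirmed nor refuted. In every version it concerns suturing time only.

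**2. Error rate if any one of the three suffices.** The plan states no success rule, so this is an assumed one, with each test at two-sided .05. Three independent tests would give 1 − 0.95³ = 14.3%. These times are not independent: OR time contains case time, which contains suturing time. The calculation therefore uses a nested model:

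- case time = suturing time + independent remainder
- OR time = case time + independent room time
- 15 per cell in 4 cells (30 v 30 by mesh), no true difference
- mesh effect from a two-way ANOVA with interaction, residual df = 60 − 4 = 56
- 200,000 simulated trials per setting

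The documents give no correlations; those below are assumed.

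| Suturing–case r | Case–OR r | Any of the three significant | OR or case significant, suturing not |
|---|---|---|---|
| 0.3 | 0.90 | 11.5% | 6.4% |
| 0.3 | 0.95 | 10.8% | 5.9% |
| 0.3 | 0.975 | 10.5% | 5.5% |
| 0.5 | 0.90 | 10.8% | 5.9% |
| 0.5 | 0.95 | 10.3% | 5.3% |
| 0.5 | 0.975 | 10.0% | 5.1% |
| 0.7 | 0.90 | 10.3% | 5.3% |
| 0.7 | 0.95 | 9.6% | 4.7% |
| 0.7 | 0.975 | 9.2% | 4.2% |

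The suturing-time test alone rejects in 4.9% to 5.1% of trials, as it should. Plain two-sample t tests (58 df) give 9.2% to 11.4% for any of the three. A separate simulation of all nine settings agreed to within about 0.4 percentage points.

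**3. Power for OR and case time.** The protocol gives neither a target difference nor an SD for these. Taking the same 30 minutes (an assumption) at 30 v 30, two-sided .05, the normal approximation to the largest SD giving 80% power is 30 / (2.802 × √(2/30)) = 30 / 0.7234 = 41.5 minutes. The noncentral t gives 40.8 minutes. For assumed SDs:

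| SD (minutes) | Power |
|---|---|
| 30 | 97% |
| 45 | 72% |
| 60 | 48% |
| 90 | 25% |

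**The case against.** The strongest reply is that the protocol already shows which outcome it means. Objective, hypothesis and sample size all name suturing time, and it is listed first. A success claim on OR time alone would contradict the stated objective, so what remains is a labelling inconsistency. This is largely right about intent, and it is why the suturing-time inference is sound. It does not remove the inconsistency: the outcome list is the formal statement of what counts as primary, and a secondary list was available and not used for these two times.

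The second reply is that the error figure depends on a rule the plan does not contain. That stands. If all three had to be significant, the same settings give about 0.3% to 1.4% error, and the cost falls on power instead. If suturing time is tested first, the primary error is 5%. A higher suturing–case correlation of 0.9 (case–OR 0.975) brings the any-one error down to about 7.8%. The range of 9.2% to 11.5% describes one permitted reading. The two harms also belong to different readings of the same silence, and only the first is expressed as an error rate.

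Third, the 30-minute target belongs to suturing time, and suturing time has no stated SD either. Both are true. The power figures in step 3 are therefore illustrations; the firm point is that power for OR and case time is not established.

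Lastly, a sponsor interested in OR efficiency might want OR time kept as primary. A fixed testing order starting with suturing time would also hold the error at .05. That is a workable alternative, but it does not make the simpler change unsound.

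**Conclusion.** The concern holds and should be fixed. The textual point is certain: three outcomes are labelled primary, one is supported by the objective, hypothesis and sizing, and nothing in the Analysis Plan ranks them, sets a success rule or divides alpha.

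The size is conditional. If any one outcome at two-sided .05 is enough, with suturing–case correlation 0.3 to 0.7 and case–OR correlation 0.90 to 0.975, the family-wise error is about 9.2% to 11.5%. Of that, 4.2 to 6.4 percentage points come from trials in which OR or case time is significant and suturing time is not. The test of suturing time is not affected. What is at stake is which results may be called primary.

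**What to change.** In Primary Outcomes, keep total suturing time as the single primary outcome, tested at .05. Move total OR time and total case time to Secondary Outcomes. In the Analysis Plan, name suturing time as the outcome of the primary ANOVA and state that the 80% power refers to it alone. The sample-size sentence already implies this; saying it outright prevents the figure being applied to the other two times.

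The cost is a wording change in two lists and a sentence in the Analysis Plan. The sample size stays at 60 and no data item is added. The one downside is that OR time and case time can no longer be claimed as primary results.

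### The Analysis Plan names no analysis for PFDI-20, and none of its stated models uses the pre-operative score, so this secondary comparison may be less precise than the data allow

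*Combined protocol and SAP*

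**What the plan says.** Secondary Outcomes lists PFDI-20 among the post-operative patient outcomes and gives its timing as "Required pre-operatively and at 6 weeks, 6, 12 and 24 months". Office Interventions and the task table repeat that schedule. Data Collection & Management lists the questionnaire among the pre-operative data, at the 6-week visit, and again under "6-month, 12-month, 24-month postoperative visit: PFDI-20".

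The Analysis Plan text does not mention PFDI-20. What it does state is:

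- **Baseline data:** "We will use descriptive statistics to show our demographic and baseline data".
- **Group comparison:** "With a continuous outcome and two categorical independent factors, a two-way" "analysis of variance will be used to evaluate differences between the groups". The factors are not named. From the context they are mesh (Y or dual flat) and route (conventional or robotic-assisted).
- **Linear regression:** "A linear regression will be done to demonstrate actual changes in surgical time attributed to each variable".
- **Logistic regression:** "We will control for LSC ASC and RA LSC ASC by performing a logistic regression".
- **Cost analysis:** operating room costs only.

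On numbers, there are four arms (two meshes by two routes), with a "plan to recruit 15 subjects to each arm, for a total of 60 subjects". The sample size is justified on suturing time. No SD, target difference or precision is given for PFDI-20.

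**The concern.** A baseline value of the same questionnaire is often the strongest single predictor available for a patient-reported score. Here it is collected from every patient, yet no stated analysis uses it. An ANOVA with only categorical factors leaves it out, the linear regression has surgical time as its outcome, and a logistic regression does not suit a continuous score. No change-score or repeated-measures analysis is described.

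What is at stake is precision, not bias: randomisation protects the unadjusted mesh comparison. Precision matters because PFDI-20 is the only patient-reported outcome listed and there are at most 30 patients per mesh group. The silence also leaves the choice between post-operative score, change score and adjusted score open until the data have been seen, at four visits.

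**Working it through.** The plan states no PFDI-20 precision figure, so there is nothing to reproduce. The check asks how much the interval for the mesh difference would change if the pre-operative score were added to the stated ANOVA.

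**Inputs**

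- Patients per mesh group: 15 per arm × 2 routes = 30 (Analysis Plan), with no losses.
- Outcome SD within mesh and route: set to 1, so results are in SD units.
- Correlation r between pre- and post-operative PFDI-20: not in the documents; 0 to 0.6 is assumed.

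**Unadjusted model (mesh, route).** Residual df = 60 − 3 = 57.

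Half-width = t(0.975, 57) × √(2/30) = 2.0025 × 0.2582 = 0.517 SD.

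**Adjusted model (mesh, route, pre-operative score).** Residual df = 56. Adjustment multiplies the residual variance by (1 − r²). Chance baseline imbalance between mesh groups multiplies the expected variance by 1 + 1/(57 − 2) = 1 + 1/55 = 1.018.

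Half-width = t(0.975, 56) × √[(2/30)(1 − r²)(1.018)], with t(0.975, 56) = 2.0032.

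| r | Adjusted half-width (SD) | Change from 0.517 |
|---|---|---|
| 0 | 0.522 | 0.9% wider |
| 0.1 | 0.519 | 0.4% wider |
| 0.2 | 0.511 | 1.1% narrower |
| 0.3 | 0.498 | 3.7% narrower |
| 0.4 | 0.478 | 7.5% narrower |
| 0.5 | 0.452 | 12.6% narrower |
| 0.6 | 0.418 | 19.2% narrower |

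**Break-even.** The squared ratio of half-widths is (1 − r²) × 1.018 × (2.0032/2.0025)² = (1 − r²) × 1.019. Setting this to 1 gives r² = 1 − 1/1.019, so r ≈ 0.136.

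**Simulation.** With normal scores and 40,000 runs at each r, the mean half-width changed by the same percentages. Coverage of the adjusted 95% interval was 0.949 to 0.952.

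**With losses.** Suppose only the 9 per arm of the sample-size statement remain, so 18 v 18. The unadjusted half-width is t(0.975, 33) × √(2/18) = 2.0345 × 0.3333 = 0.678 SD. The adjusted formula uses 32 df and a factor of 1 + 1/31. The interval is then 1.7% wider at r = 0, and narrower by 0.3% at r = 0.2, 3.0% at r = 0.3, 11.9% at r = 0.5 and 18.6% at r = 0.6. Break-even rises to r ≈ 0.18.

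**Change score, for comparison.** With equal pre- and post-operative SDs, the variance of a change score is 2(1 − r) times that of the post-operative score. At r = 0.3 this is 1.4, and √1.4 = 1.18, so the interval would be about 18% wider than with the post-operative score alone. The adjusted analysis at that r is 3.7% narrower.

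**The case against.** The strongest reply is that the plan never chose an unadjusted analysis. It is silent on PFDI-20, and the ANOVA's continuous outcome could be a change score, which would use the pre-operative value. The gap is also wider than one outcome: POP-Q and complications have no named analysis either. The size of the gain rests wholly on an assumed correlation. At r of about 0.2 or less it is negligible, and nothing in the documents places r higher, least of all after surgery for the condition measured and up to 24 months later. Losses raise the break-even slightly. Provider terms would cost further degrees of freedom that are not priced here. Separate models at each visit do not deal with missed visits or multiplicity, and a repeated-measures model would also be acceptable. Finally, this is an operating-time trial and PFDI-20 has no powered hypothesis.

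Most of this stands as a limit on the point's weight. The plan is silent rather than wrong, the correlation is unknown, and the outcome is secondary. It does not remove the point. No change-score analysis is written down, and at low correlation one would be less precise than the post-operative score alone. The unevenness of the trade also survives losses: the interval is 0.9% to 1.7% wider at r = 0, against 12% to 19% narrower at r = 0.5 to 0.6. The gap for other secondary outcomes is a reason to specify those too, not to leave PFDI-20 open.

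**Conclusion.** The concern holds. PFDI-20 is a required, repeatedly measured secondary outcome with no named analysis, and none of the stated models uses its pre-operative score. If the stated ANOVA were applied to post-operative scores, the mesh comparison would be unbiased but could be less precise than the data allow. At 30 v 30 the adjusted interval ranges from 0.9% wider at r = 0 to 19.2% narrower at r = 0.6.

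These figures assume full enrolment, a common SD, a linear relation between the two scores and no provider terms. They illustrate the effect and do not predict it. No power is quoted because the plan sets no PFDI-20 target difference. The suturing-time result is unaffected. The change should be made, but the trial does not depend on it.

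**What to change.** Add to the Analysis Plan:

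> The mesh difference in PFDI-20 at each post-operative visit will be estimated, with its 95% CI, from a linear model with mesh, route and pre-operative PFDI-20 as a covariate.

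The Randomization section says that randomisation is carried out by provider. If that means stratified by provider, include provider in the model; its cost in degrees of freedom cannot be worked out here because the number of providers is not stated.

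The cost is analysis wording only: no new data, visits or patients. If the two scores prove uncorrelated, the adjusted interval is about 1% wider at full enrolment.
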